1.0 Objectives

1.1 Study Objectives

The purpose of this study is to extend previous research (R03 CA144435) and conduct a preliminary analysis of the effect of a brief dermatologist-delivered intervention (ABC intervention) on patients' skin cancer related outcomes. The long-term goal with respect to the ABC intervention is to conduct a large-scale randomized controlled trial (RCT) with multiple clinics. Specific research aims of the study include:

The first aim examines the efficacy of the Addressing Behavior Change (ABC) intervention versus treatment as usual (TAU) during a regular dermatological visit on patient reported number of UV protective behaviors (such as use of sunscreen) and UV risk behaviors (such as number of sunburns) using a longitudinal design (3 and 6 month).

The second aim of the study will evaluate moderating factors, such as gender and history of skin cancer, and mediating factors, such as attitudes and self-efficacy, which impact the efficacy

of the intervention. The mediating and moderating variables may help to identify those individuals whom the intervention is more (or less) effective.

1.2 Primary Study Endpoints

Whether or not the ABC intervention was efficacious when delivered by dermatologists during a routine office visit compared to treatment as usual, on a number of UV protective behaviors.

1.3 Secondary Study Endpoints

Whether or not moderating factors such as gender, age, and history of skin cancer, and mediating factors, such as attitudes and self-efficacy, identify individuals for whom the ABC intervention is more or less effective.

2.0 Background

2.1 Scientific Background and Gaps

The diagnosis of melanoma (skin cancer) was estimated to have approximately 80,000 new cases in 2014, with over 10,000 persons dying from melanoma (American Academy of Dermatology, 2014). The main factor leading to skin cancer has been UV exposure (Veierod et al., 2003). Therefore, individuals can reduce their skin cancer risk (as well as its morbidity and mortality) by increasing sun protective behaviors (such as wearing sunscreen and protective clothing) and reducing both intentional and unintentional UV exposure.

Deterrence through expert delivered education approaches has been the major method of attempting to change UV risk behaviors. Effective communication between doctors (MD) and patients has been shown to enhance a variety of outcomes, such as improved health, improved patient management of chronic illness, decreased symptoms, treatment compliance, and overall satisfaction with care.

Using the ABC (Addressing Behavior Change) intervention to change UV risk behaviors is a strategy based on the principles of Motivational Interviewing (MI), which is a client centered approach originally developed in the addictive behaviors field with the intent of promoting and supporting behavior change through empathic communication. The ABC intervention emphasizes a collaborative relationship between health care providers and patients when addressing behavior change rather than MDs dictating change to a patient.

While we have developed and tested the ABC intervention during routine office visits in our R03 study, what is lacking is an examination of using the ABC intervention to address skin protective behaviors.

2.2 Previous Data

This study is a continuation of a research program examining brief dermatologist-delivered intervention on patients' skin cancer related outcomes. We had previously received a grant R03 CA144435, which found that dermatologists were very motivated to deliver the ABC intervention, were able to quickly learn the skills associated with the intervention, were able to deliver the intervention with fidelity, and showed minimal deterioration in knowledge, skills, and motivation over a 6 month period. Based on those findings, we conducted a pilot study, collecting patient data following a dermatologist visit, and found that those patients who received the ABC intervention had much higher intentions to utilize sunscreen and rated the communication with their dermatologist much higher than control patients receiving TAU. These findings together suggest the promise of the ABC intervention, which supports the need of an evaluation of the effectiveness of the ABC intervention on patient outcomes such as UV risk and protective behaviors.

2.3 Study Rationale

To date, it is unclear how effective the ABC intervention will be on patients' UV risk and protective behaviors. While we have found that dermatologists both like the ABC intervention and are able to deliver it with fidelity, and patients in a small pilot had higher intentions to utilize sunscreen and rated their dermatologist communications higher than TAU patients, it is unclear if the ABC dermatologist-delivered intervention will change patient behavior.

3.0 Inclusion and Exclusion Criteria

3.1 Inclusion Criteria

Patients must be:

- 1) Fluent in English
- 2) Mentally capable of giving consent and free of cognitive impairment (e.g., stroke, dementia, etc.)
- 3) Age 21-65 years old
- 4) A patient at Penn State Medical Center Dermatology Clinic in Hershey, PA or State College, PA, scheduled for a skin examination (either annual full body skin check or suspicious lesion) or scheduled for a Mohs surgical procedure.
- 5) Patients may include anyone who meets inclusion criteria (including previous skin cancer patients, newly diagnosed skin cancer patients, non-skin cancer patients)

Providers must:

- 1) Provide skin examinations (either annual full body skin check or suspicious lesion) or Mohs surgical procedures directly to patients (rather than supervise residents)
- 2) Treat patients that meet inclusion criteria for the study

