6.3 Waiver or alteration of authorization statements of agreement Not Applicable

7.0 Study Design and Procedures

7.1 Study Design

This study will use a longitudinal design to compare the effect of the ABC intervention on the intervention group versus the control group receiving TAU. Participants will not be randomized to a group. Instead, patients who meet eligibility criteria at PSHMC will be invited to participate at the intervention site, and current patients who meet eligibility criteria at the clinic in State College will be invited to participate at the control site.

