7.2 Study Procedures

Subjects will be recruited from two sites: 1) Penn State Hershey Medical Center Clinic in Hershey (PSHMC), which will serve as the intervention site where patient participants will receive the ABC interventions, and 2) Penn State Medical Group in State College (State College), which will serve as the control site where patient participants will receive TAU.

- 1) Participation will begin when participants are screened for eligibility over the phone.
- 2) Participation will continue for subjects when they arrive at either PSHMC or State College for an appointment with a participating physician that will include a skin check (either annual full body skin check or suspicious lesion) or Mohs surgical procedure (please see the recruitment section for a step-by-step process of how eligible participants will be obtained). A skin check involves the physician checking the patients' skin for any growth or mark that could potentially become cancerous. Patients at the control site will be receiving TAU for their skin check; patients at the intervention site will receive a normal skin-check, combined with the ABC-intervention (see uploaded information sheet). The audio recordings which will be done at both the control and intervention sites for all participants will be used to compare the information patients receive from their doctor during the course of a skin check.
- 3) Participants will be asked to arrive 25 minutes prior to their appointment so the informed consent process may take place prior to any study related procedures being conducted. After they check in, they will be greeted by a research assistant in the waiting room and directed to a private area within the clinic. The research assistant will be accessible while the participant completes the survey to answer questions that may arise. The baseline survey will assess demographic information, history of skin cancer, UV risk behaviors, perceived risk of skin cancer, dermatologist communication, attitudes about sun protection behavior, self-efficacy about sun protective behaviors, etc. (Please refer to Measures document for full questionnaire).

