- 4) As part of the surveys, participants will be asked to provide the contact information of a friend or relative that we could contact in the event that we are unable to locate the individual for the 1-month and 3-month follow-up surveys. Phone and email/letter scripts are included in the recruitment documents. We will attempt to call the "collateral contact" up to 2 times, and then will send a letter or email if we cannot reach them by phone. Participants will be reminded of the following when they log on to the survey: "By completing the following survey you are agreeing to take part in this research study. If you have any questions about

the survey or your participation, please contact project coordinator, [name], at [contact] or [contact]".

- 5) The patient will then proceed to their appointment with a dermatologist. At the intervention site, the provider who has been trained to deliver the ABC intervention will do so during the skin exam. During the appointment at the intervention site, providers will provide their patients with a handout (as a small card and/or magnet) which summarizes what they discussed during the appointment regarding sun protection (CURE Method Tips – see uploaded document). At the control site, patients will receive TAU, with no ABC intervention. All patient participant appointments are to be audio recorded and by consenting to the study, patients are consenting to be audio recorded. A research assistant will accompany the patient into the exam room to audio record the visit. Only providers who have taken the appropriate training will have patients identified to participate in this study (intervention). Providers at both the intervention and control sites will be consented prior to any audio recordings being done, as explained in section 5.1.1. Research assistants will later listen to and code the data to determine if the components of the ABC intervention were delivered with fidelity. Control sessions will be recorded and coded using the same criteria to document those patients who did not receive elements of the ABC intervention. The recordings will be coded with the patient's study number and will be destroyed per PSHMC IT Security Group policy as soon as data is coded from their analysis. The participant and the provider will be reminded prior to the recording to not use names or other identifying information during the recording.

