25.3 Aim 1: Evaluate efficacy of the ABC intervention

[name] (Co-I) will conduct all outcome analyses in order to avoid any bias. First a 2 (Group: ABC vs. Controls) x 3 (Time: baseline, 3 & 6 mo. follow-up) Mixed ANOVA will be conducted to test the intervention on a given outcome variable (e.g., use of sun protection). First, we expect to observe a main effect of Group with the highest reports of sun protection (and lowest reports of UV risk behaviors) occurring in our ABC condition. Second, we anticipate observing a Group x Time interaction with no differences between the groups at baseline but differences (lower risk in the ABC group) at each of the follow-ups. He will also assess the scientific and clinical significance of the effects utilizing the magnitude estimation approach described by Jaccard. Specifically, statistical significance refers to the case when the null hypothesis is rejected, whereas magnitude estimation approaches emphasize the size of the effect. To utilize magnitude

estimation approaches, the researcher must specify an a priori effect size that differentiates a trivial effect from a meaningful effect. If the effect size observed is less than the criterion for meaningfulness, then the result is deemed nonsignificant, even if the null is rejected. We will use Cohen's d statistic to assess clinical significance of the main effects and interactions. We will define an effect as clinically and statistically significant to the extent that the d is greater than or equal to .20.

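### Mohs-surgery patients are pooled with skin-check patients and visit type is not in the Aim 1 model, so Group x Time would be biased if both the Mohs share and the Mohs time course differ

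*Combined protocol and SAP*

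**What the plan says.** **Question.** Protocol 1.1 sets ABC against "treatment as usual (TAU) during a regular dermatological visit". The primary endpoint in 1.2 is worded the same way: "Whether or not the ABC intervention was efficacious when delivered by dermatologists during a routine office visit compared to treatment as usual".

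**Delivery.** Protocol 7.2 states that "patients at the intervention site will receive a normal skin-check, combined with the ABC-intervention" and that, at the intervention site, "the provider who has been trained to deliver the ABC intervention will do so during the skin exam". It does not describe ABC at a Mohs visit.

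**Who is enrolled.** Section 3.1 takes patients "scheduled for a skin examination (either annual full body skin check or suspicious lesion) or scheduled for a Mohs surgical procedure". Sections 4.1 and 7.2 repeat both visit types. No quota, matching or stratification by visit type is given.

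**Allocation.** Section 7.1: "Participants will not be randomized to a group". Hershey is the intervention arm and State College the control arm.

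**Analysis.** SAP 25.3 specifies a 2 (Group) x 3 (Time) mixed ANOVA with no covariates, and calls an effect meaningful at d of .20 or more. Visit type is named in neither aim. The nearest variable, history of skin cancer, is a moderator for Aim 2 (1.3, 25.4).

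**The concern.** A Mohs patient has skin surgery on the day of the baseline survey. Sun behaviour over the following months may move for that reason alone, in either arm. Group x Time removes a stable difference between the clinics. It does not remove a difference in change that comes from a different mix of visit types. With one clinic per arm and no randomisation, nothing in the design makes the mix equal, and nothing in the Aim 1 model adjusts for it or would reveal it.

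Two things are at stake. A change related to surgery could be read as an ABC effect, or could hide one. And if ABC itself works differently at Mohs visits, the pooled estimate is a case-mix average rather than an answer about routine visits, even with equal shares.

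**Working it through.** The plan gives no Mohs share and no expected change by visit type, so it has no figure of its own to reproduce here.

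**Inputs from the documents:** planned enrolment 227 (protocol 9.1 and 16.0), or 227/2 = 113.5 per arm if split evenly; 100 per clinic in the second cohort (4.2); threshold d = .20 (SAP 25.3).

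**Assumptions:** g = difference in Mohs share between clinics; m = extra change in Mohs patients regardless of ABC, in SD, of either sign; baseline to follow-up correlation 0.5; two-sided 5% test.

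**Step 1, bias.** Without ABC, mean change in a clinic is (skin-check change) + (Mohs share) x m. Subtracting one clinic from the other leaves g x m.

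| g | m | bias (SD) |
|---|---|---|
| 0 | any | 0 |
| any | 0 | 0 |
| 0.20 | 0.5 | 0.10 |
| 0.30 | 0.67 | 0.20 |
| 0.40 | 0.5 | 0.20 |
| 0.40 | -0.5 | -0.20 |
| 0.50 | 0.40 | 0.20 |

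For g from 0.10 to 0.50 and m from 0.2 to 0.8 the bias runs from 0.02 to 0.40 SD. Negative m mirrors this.

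**Step 2, false-positive rate.** The SD of change is sqrt(2(1 - 0.5)) = 1, so SE = sqrt(2/113.5) = 0.133.
- Bias 0.10: 0.10/0.133 = 0.75; rejection probability 11.7%.
- Bias 0.20: 0.20/0.133 = 1.51; rejection probability 32.5%.
- Bias 0.20 with correlation 0.3 or 0.7: about 25% or 49%.
- Bias 0.20 with 100 per arm, correlation 0.5: about 29%.

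**Step 3, simulation.** 100 per clinic, no ABC effect, correlation 0.5, 4,000 runs, contrast = mean of two follow-ups minus baseline.

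| Mohs shares | m | bias, rate as planned | bias, rate with visit type x Time |
|---|---|---|---|
| 40% v 10% | 0 | 0.00, 5% | 0.00, 5% |
| 20% v 20% | 0.5 | 0.00, 5% | 0.00, 5% |
| 40% v 10% | 0.5 | 0.15, 22% | 0.00, 5% |

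The first two rows show that both conditions are needed. The third shows that the added terms remove this bias.

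**Step 4, price of adjustment.** Taking visit type as Mohs versus skin check, variance inflation is 1/(1 - phi²), with phi² = (g/2)²/[p(1 - p)] and p the mean share.
- 30% v 10%: phi² = 0.01/0.16 = 0.0625; inflation 1.07.
- 40% v 10%: phi² = 0.0225/0.1875 = 0.12; inflation 1.14.
- 50% v 0%: phi² = 0.0625/0.1875 = 0.333; inflation 1.50.

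A skin-check-only analysis at 40% v 10% keeps 60 and 90 of 100. Its variance ratio is (1/60 + 1/90)/(2/100) = 1.39.

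**The case against.** The strongest reply is that neither g nor m is known. Mohs procedures are on the schedule when patients are recruited, with letters going out some 2-4 weeks ahead, and the baseline survey precedes the appointment. Any response to the diagnosis may already be in the baseline, where Group x Time treats it as a level difference. Patients who already protect themselves well have less room to improve, so m could be zero or negative. This stands: no size or direction of bias can be claimed.

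A reader might infer that unequal Mohs shares alone bias Group x Time. They do not, as the simulation with m = 0 shows. A reader might also infer that the pooled estimate cannot answer the routine-visit question. That goes too far. The term is not defined, the broad population is stated openly, and with few Mohs patients the pooled and skin-check estimates would nearly coincide.

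History of skin cancer gives partial cover. Entered as a factor under 25.4, it would absorb some differential change. But it belongs to Aim 2 and is a proxy for visit type. A reader might suppose that it is a yes/no item mixing current surgery with old cancers; the documents do not give its coding, and the measures document is not in the file.

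Finally, protocol 1.1 calls this a preliminary analysis, and visit type is one of many differences between two clinics. That limits what the change achieves, but it is no reason to leave out a variable visible at recruitment.

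**Conclusion.** The concern holds conditionally. The documents establish the gap: a routine-visit question, two kinds of index visit pooled, allocation by clinic, and an Aim 1 model without visit type or any sensitivity analysis for it. They do not establish a bias. That requires both a different Mohs share and a different time course in Mohs patients unrelated to ABC, and neither can be estimated from the text. Under plausible but assumed values the bias could reach the plan's own threshold with no ABC effect at all; it could equally be nil or run against ABC. The error rates also depend on the assumed correlation and an even split of 227. Confidence is high in the omission and low in the size. This is a change that should be made, not a fatal flaw.

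**What to change.** 1. Store visit type (annual check, suspicious lesion, Mohs) from the schedules that the coordinator already reviews under protocol 4.1, and report its distribution by site. Whether it is already collected cannot be checked from the file.
2. In SAP 25.3, add visit type and visit type x Time to the Aim 1 model.
3. Prespecify a skin-check-only analysis to carry the routine-visit conclusion. Rely on it if one clinic enrols almost no Mohs patients, because adjustment then has no overlap to work with.
4. Reconcile the parts of 7.2 that describe ABC only at the skin exam with the parts of 3.1, 4.1 and 7.2 that enrol Mohs patients.

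**Cost.** SAP wording, one stored field, and some precision: variance inflation of about 1.07 to 1.14 for moderate imbalance, and up to 1.50 in the case worked above where all Mohs patients come from one clinic. The skin-check-only analysis has a smaller sample. Other differences between the two clinics remain confounded with the intervention.

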3.2 Exclusion Criteria

Patients will be excluded if they:

- 1) Do not meet inclusion criteria as stated above
- 2) Have psoriasis (as a recommended treatment of psoriasis is intentional UV exposure)
- Have had previous exposure to the ABC intervention during the R03 at Penn State Hershey Medical Center in 2010 or during data collection for this study during Spring 2016

Providers will be excluded if they:

- 1) Only supervise residents and do not provide skin exams directly to patients
- 2) Do not treat patients that meet inclusion criteria for the study

3.3 Early Withdrawal of Subjects

3.3.1 Criteria for removal from study

The only reasons participants will be removed from the study is if they fail to give or withdraw consent for participation.

3.3.2 Follow-up for withdrawn subjects

N/A – withdrawn subjects are simply dropped from the participant pool, and no further contact will be made.

4.0 **Recruitment Methods**

4.1 Identification of subjects

The first step in identifying potential patient participants will be to have the PSHMC Dermatology research nurse coordinator review appointment schedules at both sites (Hershey – intervention; State College – control) to see which patients are scheduled to receive skin checks (either annual full body skin check or suspicious lesion) or Mohs surgical procedures at upcoming appointments. The PSHMC Dermatology research coordinator at the clinics will either: 1) call potential patient participants and invite them to participate via the phone, or 2) send a letter to these patients approximately 2-4 weeks prior to their scheduled appointment, explaining the research and inviting them to call the research team to obtain more information or to email/call the PSHMC research team within approximately 2 weeks if they are not interested in learning more about the study.

Providers interested in participating at Penn State Hershey Medical Center (PSHMC) and State College will be randomly selected from the departments (up to n=10 per site).

4.2 Recruitment process

Recruitment of Patients:

- The PSHMC Dermatology research nurse coordinator will either: 1) call potential participants and invite them to participate via the phone, or 2) send a pre-notification letter to these patients approximately 2-4 weeks prior to their scheduled appointment, explaining the research and inviting them to call the research team to obtain more information or call/email within approximately 2 weeks if they are not interested in learning more about the study.
- 2) For those receiving the pre-notification letter, after approximately 2 weeks, the patients who did not indicate disinterest in the study or contact PSHMC for more information, will be called by a PSHMC research assistant and will be formally invited to participate in the study. For both individuals who contact the research team directly and those who are contacted due to not declining, will follow the same procedures: If they are interested, the research assistant will obtain verbal consent to screen patients to see if they qualify for the study based on the inclusion/exclusion criteria. If they are eligible, they will then be formally invited. Potential participants interested in the study will be asked to arrive 25 minutes early for their appointment so that the consent form may be reviewed with them in its entirety and signed informed consent can be obtained in a private area of the clinic prior to the completion of the brief baseline survey. A log will be kept of all *de-identified* patients contacted via phone who declined participate when approached in the clinic (example: adult male #1 refused study due to time commitment).
- 3) For those who are called and invited to participate over the phone by a PSHMC research assistant, the research assistant will explain the study, and if the patient is interested, the research assistant will obtain verbal consent to screen patients to see if they qualify for the study based on the inclusion/exclusion criteria. If they are eligible, they will then be formally invited. Potential participants interested in the study will be asked to arrive 25 minutes early for their appointment so that the consent form may be reviewed with them in its entirety and signed informed consent can be obtained in a private area of the clinic prior to the completion of the brief baseline survey. A log will be kept of all de-identified patients contacted via phone who declined participate when approached in the clinic (example: adult male #1 refused study due to time commitment).
- 4) In the first cohort in Spring 2016, we enrolled 27 participants who qualified after completing the screening. For the second cohort in Spring 2017, we plan to enroll an additional sample of 200 (100 per site). Based on the response rate of the first cohort in Spring 2016, we will invite up to 770 participants in Spring 2017. Once the target enrollment of 200 total (about 100 per site) is obtained, we will discontinue recruiting. The study will be split into 2 cohorts

– one taking place in Spring 2016 (n=27) and the other taking place in Spring 2017 (target n=200).

- 5) Participants who are interested and who qualify to participate will either: 1) be asked on the phone for their email address in order to send a copy of the consent form and reminder to arrive at their scheduled appointment 25 minutes prior to their scheduled time, or 2) receive a copy of the informed consent and a letter by mail reminding them to arrive at their scheduled appointment 25 minutes before their scheduled time to perform the written informed consent process and to complete the baseline survey. Participants will also be called 1-3 days before their scheduled appointment to remind them to arrive 25 minutes early (see reminder phone script).
- 6) 1-month and 3-month follow-up surveys will be conducted online to reduce burden and allow participants to complete them from home. Participants can request mailed, paper-based surveys if they do not want to complete the online version of the survey. Paper-based cover letter and surveys will be mailed to participants' homes along with prepaid return envelopes. Both the online version of the follow-up surveys as well as the hardcopy surveys (which will include identical questions/prompts as the REDCap survey), will include the text at the beginning of the survey that states "By completing the following survey you are agreeing to take part in this research study. If you have any questions about the survey or your participation, please contact project coordinator, [name], at [contact] or [contact]". Participants will receive an invitation email, up to 5 reminder emails, and up to 3 reminder phone call attempts to complete each survey. During the baseline survey, participants will also be asked if they would like to receive SMS text message reminders to participate in the follow-up surveys. If participants opt into receiving SMS text message reminders, they will receive 2 text message reminders for each survey along with all other contact methods.

Subjects will be informed in the consent process:

"You should be aware that it is illegal in the Commonwealth of Pennsylvania to text while driving. It is also dangerous to pay attention to your cellular phone while driving, walking, or doing any activity that requires your attention. You should continue to exercise good judgment on this while participating in this study."

Please note: Mailed hardcopy surveys/letters will only be offered to individuals who indicate that they do not have access to the internet, not as an option for all participants. With the timeframe between the 1-month survey and the 3-month survey being shorter, we do not want there to be any overlap of surveys if participants are slow to mail back their responses.

Recruitment of Physician Interventionists:

- The dermatologists from the intervention site will undergo 1 session of training to deliver the ABC intervention, following the same protocol developed and used in the R03 study. A weekly scheduled journal club meeting will be cancelled and this training will take the place of it in the evening (instead of morning) and will require no additional time commitment from the dermatologists to participate in the training or study.
 - a. The first component of training will involve learning to deliver each of the 6 components of the intervention. Patient interactions will be demonstrated by the study staff.
 - b. The second component will involve role plays. The physicians will practice implementing the intervention on research assistants who will pose as mock patients.
 - c. The third component will involve supervision and feedback. Drs. [name] and [name] will observe the physicians while they deliver the ABC intervention to patients. They will then provide feedback privately.
 - i. For Spring 2017, a training booster will take place. This will include component C (supervision) in order to ensure there is consistency in intervention delivery.
- 2) Up to 10 providers from the intervention site and up to 10 providers from the control site will be randomly selected to participate. If they agree, intervention dermatologists will give

verbal consent after reviewing the Summary Explanation of Research provided by a member of the research team during the scheduled Dermatology Department meeting, and control site dermatologists will give verbal consent prior to the recruitment of patients.

3) The dermatologists at the control site will deliver treatment as usual (TAU) to their patients, and will not undergo the training and supervision.

